Nepal being an Asian country is also in the region to have increased cases of cholangiocarcinoma and need rigorous scientific studies to generate evidence to prepare interventions on its prevention and treatment. Cholangiocarcinoma being the major contributing factor for the death of the humans, this needs early diagnosis and treatment system to intrude the increasing mortality and morbidities. Studies should be conducted in its risk factors, disease status, occurrence and other factors so that such studies are considered to estimate the prevention and management of such deadly diseases.

The studies on this sector is in dearth and is in great need of the involvement of academia, medical centers and different institutions. Such studies will provide evidence to plan several interventions for its better and efficient prevention and treatment option.

B.3. Research hypothesis (if applicable):

NA

B.4. Objectives of the research:

General objective (s)

The aim of the study is to assess the clinico-demographic profile of the patient with cholangio-carcinoma undergoing ERCP in Dhulikhel Hospital.

Specific objective(s):

This study holds the objective,

- To identify clinical profile of the patient with cholangio-carcinoma undergoing ERCP
- To describe the demographic profile of the patient with cholangio-carcinoma undergoing ERCP
- To measure the outcome of ERCP procedure in them.
- To identify the association between demographic variable and clinical presentation of the patient with cholangio-carcinoma undergoing ERCP

B.5. Study site and justification:

The study will be conducted in the Endoscopy unit of the Internal medicine department of Dhulikhel Hospital. This hospital has provided services to more than 50 out of 75 districts of the country. It provides services to about 2.7 million people from Kavrepalanchowk, Sindhupalchowk, Dolakha, Lalitpur, Kathmandu, Sindhuli, Ramechhap and other surrounding districts per-year. In Nepal ERCP procedure has been limited to very few Tertiary centers and Dhulikhel Hospital is the pioneer institute to provide the ERCP procedure (since 2011) in the nation. This procedure is mainly performed for the indication of choledocolithiasis, obstructive Jaundice, acute biliary pancreatitis, cholangiocarcinoma, etc. In 2019 only, a total of 1352 patients had undergone ERCP in Dhulikhel Hospital as per the monthly ERCP report book obtained from the Department of Endoscopy of Dhulikhel Hospital.

B6. METHODS/ METHODOLOGY:

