B.6.1 Research Methods (Cross in the appropriate box)

a) Qualitative Research Quantitative Research c) Mixed Research

B.6.2. Study design:

This is a quantitative, retrospective, descriptive cross-sectional observational study.. The outcome and the exposure will be measured at the same time as a snapshot.

B.6.3. Study Variables

The study variables will be the socio-demographic variables and the clinical details of the study participants.

B.6.4. Expected outcomes of the research

The expected outcome of the research is to present a clinical finding of this under studied clinical area in Nepal. Furthermore, this will be a reference for the future researchers to conduct further studies on this sector to enhance the prevention, management and the treatment services.

B.7 STUDY POPULATION AND SAMPLE

B.7.1. Participants/ study population:

Patients with cholangiocarcinoma who had undergone ERCP in Endoscopic Department of Dhulikhel Hospital. The patient's information will be obtained from patients' medical records from the outpatient and inpatient department of Dhulikhel Hospital. Thus, the person will not be contacted directly for the data collection.

B.7.2 Selection criteria:

Inclusion criteria:

- All the participants with cholangiocarcinoma had undergone ERCP
- above 18 years of age.

Exclusion criteria:

- ERCP failed cases

B.7.3. Sampling method/ technique:

We will do purposive sampling from the eligible list obtained from the medical records.

B.7.4. Sampling Unit:

The sampling unit is the patient with cholangiocarcinoma who had undergone ERCP.

B.7.5 Sample size determination:

All the eligible cases listed in the medical record of Dhulikhel Hospital from January 2017 to January 2023. Hospital records showed approximately 75 cases of cholangiocarcinoma per year. So, we will conduct a total population sampling with an estimated sample size of 375.

B.8. Procedure:

First of all, the researcher will get formal approval for data collection in the institution.

- After ethical clearance, data will be collected through a case sheet of the patient and record of ERCP procedure at the department using prepared Per forma.
- Data of procedure outcome will be collected via call to the patient. Before collecting information from the respondent, they will be informed about the objective of the study and will be assured of privacy and volunteering participation.

B.8.1. Data Collection Tools/ Measures:

- Clinical Proforma will be used to collect data

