 - Part I: Socio-Demographic information of patient
 - Part II: Information related to Clinical profile of patient
 - Part III: outcome of ERCP procedure
- The data will then be entered into Microsoft Excel for further data management.

B.8.2. Pretesting

The proforma will be pretested entering about 10 cases so that we can further modify the proforma.

B.8.3. Validity and Reliability of tool

The tool will be the proforma and this will be based on other literatures and as per the experts suggestion. Indeed, the principal investigator is the physician (expert) to perform this procedure in Nepal and other team members have some kind of exposure in this sector.

B.9. Plan for specimen/data management:

(a) Data Processing

- Collected data will be stored in a file to prevent loss or damage.
- Data will be coded and entered in Microsoft Excel Sheet and will be transferred to the Statistical Program for Social Science (SPSS) for further analysis.

(b) Presentation of Data

- Data will be categorized on the basis of research objectives.
- The study will present the descriptive statistics and other details of the variables.

B.10. Plan for data analysis:

B.10. a. SPSS (Statistical Program for Social Science) version 25.0 will be used for descriptive as well as inferential statistics.

B.10. b. Statistical tests: Descriptive statistics (mean, frequency, standard deviation and percentage) will be applied. For inferential statistics, Chi-square test will be used for the analysis of the categorical data while, t-test or correlation will be done for the continuous variables.

B.11. Potential Biases:

There may be some confounders that will direct to the bias of the study. The information in the confounders will be collected and if required will be adjusted in the data analysis.

B.12. Limitations of the study:

- This is not a common disease, so the sample size of the eligible participants is limited.
- The retrospective study nature of this study may not allow us to incorporate as much information as we are seeking. However, future research may address these issues.

B.13. Plan for supervision and monitoring:

- Data will be collected by the co-authors
- Supervision and monitoring will be done by Principal Investigator and the research team

B.14. Plan for dissemination of the research:

The research will be disseminated to:

- Conferences
- Publication in one of the index peer review journal

B.15. DATA AND SPECIMEN BANKING AND/OR SHARING

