5. EUS FNA

- a) Yes
- b) No

6. If Yes

- 1) Positive
- 2) Negative

7. Brush cytology

- a) Yes
- b) No

8. If Yes

- 1) Positive
- 2) Negative

9. Intra ductal biopsy

a) Yes

b) No

10. If Yes

- 1) Positive
- 2) Negative

11. Surgical operability

- a. Operable
- b. Non-operable
- c. Unknown

12. Lab reports

- a) Total bilirubin.....
- b) Direct bilirubin.....
- c) ALP.....
- d) GGT.....
- e) AST.....
- f) ALT.....
- g) PT.....
- h) INR.....

13. Type of growth

- a. Distal
- b. Hilar

1) Bismuth-I

2) Bismuth-II

3) Bismuth-III

4) Bismuth-IV

5) Bismuth-V

Part 3. Outcome of ERCP procedure

14. Type of stent used in ERCP:

- a) Plastic stent
- b) Metal stent (SEMS)

15. Outcome of Stenting

- a) Immediate
- b) Failed Stenting
- c) Successful stenting

16. Complications

- a) Perforation
- b) Bleeding
- c) PEP
- d) PEC

17. If PEP done

- 1) Within 2 weeks
- 2) After 2 weeks

18. If PEC done

- 1) Within 2 weeks
- 2) After 2 weeks

19. Restenting

- a) Yes
- b) No
- 1) Within 1 month
- 2) Within 2 month
- 3) Within 3 month

20. Radio- Frequency Ablation

- Yes
- No

21. Survival Rate

- a) < 1 month
- b) 3-6 month
- c) 6 month- 1 year
- d) >1 year

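### Excluding failed ERCP cases selects patients on the outcome that the third objective sets out to measure, so the reported success rate is overstated

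*Combined protocol and SAP*

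**What the plan says.** B.4 lists four specific objectives. The third is "To measure the outcome of ERCP procedure in them", where the last word refers to patients with cholangiocarcinoma undergoing ERCP. B.7.1 defines the population as "Patients with cholangiocarcinoma who had undergone ERCP in Endoscopic Department of Dhulikhel Hospital". The inclusion criterion in B.7.2 is "All the participants with cholangiocarcinoma had undergone ERCP", together with an age limit. None of these requires that the procedure succeeded.

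The single exclusion criterion in B.7.2 is "ERCP failed cases". The term is not defined, and nothing in the plan provides for counting or reporting the patients removed under it.

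The data collection tool (B.8.1) has a section "Part III: outcome of ERCP procedure". In the proforma, item 15 of that part, "Outcome of Stenting", offers both "Failed Stenting" and "Successful stenting". B.11 (potential biases) speaks only of confounders. B.12 (limitations) speaks only of the small number of eligible patients and the retrospective design.

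**The concern.** Whether ERCP failed is a result of the procedure. Using it as an eligibility rule conditions the sample on the outcome that the third objective asks about. The plan sets out to record failure while removing patients because they failed.

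A success rate from this sample would describe patients in whom ERCP worked, but the objective, population and inclusion criterion all invite the reader to apply it to everyone undergoing ERCP. Complications (item 16) and survival (item 21) in the excluded patients would also go unrecorded. For the first two objectives, the clinical and demographic profile would describe a narrower group than the one named. The adjustment for confounders foreseen in B.11 cannot restore patients whose records were never abstracted. The results are meant as a reference for later researchers (B.6.4) and a baseline for interventions (C1), so an overstated success rate would be carried forward.

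**Working it through.** **Inputs.** The documents give no ERCP failure rate and no stenting failure rate, so both are assumed and varied:

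- *f*: share of patients with attempted ERCP who are excluded as failed; 5%, 10% or 20%.
- *g*: share of the retained patients in whom stenting failed; 0%, 5% or 10%.
- Stated sample size, used only for scale: 375 (B.7.5).

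**The plan's own figure.** The plan gives no success rate to reproduce. Its 375 is a count of cases: 75 per year × 5 = 375. The stated window of January 2017 to January 2023 is six years, which gives 75 × 6 = 450. The text does not attribute the difference of 75 to excluded failures, so it says nothing about *f*.

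**Formulas.**

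- Reported success = 1 − g
- Success among all patients attempted = (1 − f)(1 − g)
- Overstatement = (1 − g) − (1 − f)(1 − g) = f(1 − g)

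The overstatement is above zero whenever any failed case is excluded and stenting succeeds in at least some patients.

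**Reading A: failure includes failed stenting.** No failed stenting remains in the sample, so g = 0 and reported success is 100% whatever the data. The rate among all attempted is 95%, 90% or 80% for f = 5%, 10% or 20%.

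**Reading B: failure means failed access or cannulation only.** With g = 5%:

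| f | Reported | All attempted | Overstatement |
|---|---|---|---|
| 5% | 95% | 0.95 × 0.95 = 90.25% | 4.75 points |
| 10% | 95% | 0.90 × 0.95 = 85.5% | 9.5 points |
| 20% | 95% | 0.80 × 0.95 = 76% | 19 points |

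Over g from 0% to 10%, the overstatement is 4.5 to 5 points at f = 5%, 9 to 10 at f = 10%, and 18 to 20 at f = 20%.

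**Against sampling error.** For a 90% rate at n = 375, the half-width of the 95% confidence interval is 1.96 × √(0.9 × 0.1 / 375) = 0.030, or 3.0 points. Even at f = 5% the overstatement is larger than this, and a larger sample would not reduce it.

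**Complications.** The rate among all attempted is (1 − f)·c₁ + f·c₂, where c₁ is the rate in retained patients and c₂ the rate in failed cases. With assumed values c₁ = 10%, c₂ = 30% and f = 20%, this is 0.8 × 0.10 + 0.2 × 0.30 = 14%, against 10% reported. If c₂ = c₁ there is no difference. The documents give neither rate, so direction and size are open here.

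**The case against.** The strongest reply is that Reading A is the less likely one. The proforma keeps a box for failed stenting, which would have no purpose if such patients were excluded. On Reading B, stenting success among completed ERCPs is a legitimate conditional figure, and B.10 does not commit to a rate per attempt. The defect would then be an undefined term and an unstated denominator. This has force: the 100% case should not be taken as the expected one. It does not remove the problem, because B.4, B.7.1 and B.7.2 all name patients undergoing ERCP without a success condition, and the rate for that group cannot be obtained on either reading.

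Other points stand in part:

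- **Size.** It rests wholly on assumed rates. If a patient whose first ERCP failed and second succeeded is retained, *f* is smaller than the failure rate per procedure. The plan does not say how such patients are classed.
- **Restenting.** Stent type (item 14) and restenting (item 19) apply only to patients who received a stent, so the exclusion hardly distorts them.
- **First two objectives.** The effect is a restricted population, not an outcome bias. It is plausible but undocumented that failed cases differ in anatomy or disease.
- **Item 15.** It lists an immediate category beside the two results, mixing timing with outcome. This may be lost nesting in the extracted text and should be checked on the form itself. The main point does not depend on it.
- **Priority.** The general aim is a clinico-demographic profile. Measuring the outcome is nevertheless one of four stated objectives.

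**Conclusion.** The concern holds and should be fixed before records are abstracted. As written, the third objective cannot be met for the population it names. The direction is certain for technical success: it is overstated on both readings whenever any failed case is excluded. The size cannot be found from the documents. Under assumed exclusion of 5% to 20% of patients and stenting failure of 0% to 10% in the rest, it is about 4.5 to 20 percentage points. For complications and survival, information is lost but no direction can be claimed.

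**What to change.** 1. Delete the exclusion in B.7.2 and include every adult with cholangiocarcinoma in whom ERCP was attempted in the window. State which procedure counts when a patient had more than one.
2. Recode item 15 into mutually exclusive results: ERCP or cannulation failed; ERCP done but stenting failed; stenting successful. Record any timing separately.
3. In B.10, name all patients attempted as the denominator for success and complications. Give figures among completed ERCPs as secondary.
4. Allow a not-applicable code for items that may be unobtainable after failed access, such as brush cytology and intraductal biopsy (items 7 to 10) and stent type (item 14).

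If failed cases truly cannot be abstracted, the minimum is to define ERCP failure, restate the third objective as conditional on a successful ERCP, and report the number excluded. That is honest but answers a narrower question.

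**Cost.** One protocol line, a sentence in B.10 and small proforma changes, which B.8.2 already allows for after pretesting. If 375 is the number left after exclusion, total patients would be 375/0.95 = 395, 375/0.90 = 417 or 375/0.80 = 469 for f = 5%, 10% or 20%. That is about 20, 42 or 94 more charts, from sources already in use. The reported success rate will be less favourable. Leaving the change until later would mean a second chart review.

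### No index ERCP or time origin is defined, so patients first treated before 2017 can enter only if they survived into the window, and survival counted from the first ERCP would be overstated

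*Combined protocol and SAP*

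**What the plan says.** All places are in the combined protocol and SAP.

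- **Window (B.7.5):** "All the eligible cases listed in the medical record of Dhulikhel Hospital from January 2017 to January 2023". The same section adds "Hospital records showed approximately 75 cases of cholangiocarcinoma per year" and "So, we will conduct a total population sampling with an estimated sample size of 375".
- **Entry (B.7.2):** inclusion is "All the participants with cholangiocarcinoma had undergone ERCP", plus age above 18. The only exclusion is "ERCP failed cases". Neither an earlier ERCP nor an earlier stent bars entry.
- **Unit and source (B.7.4, B.7.1):** the unit is the patient, with no index procedure named. Records come from both outpatient and inpatient departments.
- **Site history (B.5):** "Dhulikhel Hospital is the pioneer institute to provide the ERCP procedure (since 2011) in the nation".
- **Outcomes (B.4 and proforma Part 3):** measuring the outcome of ERCP is the third of four specific objectives. Item "19. Restenting" is yes or no, with timing options up to three months. Item 21 records survival in bands. Neither says from which procedure time runs, and no proforma item asks for an ERCP date or a previous stent.
- **Analysis (B.10, B.11):** descriptive statistics, chi-square, t-test or correlation, with adjustment for confounders if needed. No delayed-entry method is planned.

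**The concern.** Take two patients first stented at this hospital in 2016. One dies that year and can never be listed in the window. The other is alive in 2017, is seen again and meets every criterion in B.7.2. The second is in the study because of having survived. This is left truncation. Counting each patient once removes duplicates but does not remove the selection.

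The plan has neither of the usual safeguards, which are an entry rule tied to a first procedure or an analysis that allows for late entry. Items 19 and 21 could therefore be summarised over a mixture of new cases and selected survivors. Because no origin is set, two abstractors could also date the same patient's survival from different procedures. Any resulting bias is systematic and does not shrink as patients are added.

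**Working it through.** **The plan's own figure.** January 2017 to January 2023 is about 6 years, and 75 × 6 = 450. The stated 375 equals 75 × 5. That mismatch is a separate matter. I use 450 new cases because it follows from the stated window and rate.

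**Inputs from the documents:** about 75 cases a year, a window of 72 months, and ERCP since 2011 (taken as 72 months before the window opens).

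**Assumptions, not in the documents:** the 75 are new patients arriving at a constant rate (75/12 = 6.25 a month); survival is exponential with median m of 3, 6, 9 or 12 months; time to a repeat ERCP is exponential with median 4 months.

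**Formulas.** Death rate h = ln 2/m; repeat rate r = ln 2/4 = 0.1733 a month.

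1. Earlier patients alive in January 2017: N = (6.25/h) × (1 − e^(−72h)).
2. Probability of a repeat ERCP before death: p = r/(r + h).
3. Entrants by repeat ERCP: Np. If any visit counts as listing, the entrants are N.
4. Share of sample: entrants/(450 + entrants).
5. One-year survival from first ERCP is e^(−12h) in new cases. In entrants by repeat ERCP, total survival is the sum of three waiting times: first ERCP to January 2017 (rate h), then to the repeat (rate r + h), then to death (rate h). Call the proportion beyond 12 months q, evaluated numerically.
6. Pooled one-year survival: (450e^(−12h) + Np × q)/(450 + Np).

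**Worked case, m = 6.** h = 0.1155, so N = 54.1, p = 0.60 and Np = 32.5. The share is 32.5/482.5 = 6.7%. With q = 0.731, pooled one-year survival is (450 × 0.250 + 32.5 × 0.731)/482.5 = 28.2%, against 25.0% in new cases.

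| Median survival (months) | Alive Jan 2017 | Enter by repeat ERCP | Share | Share if any visit counts | One-year survival, new cases | Pooled, repeat ERCP | Pooled, any visit |
|---|---|---|---|---|---|---|---|
| 3 | 27.1 | 11.6 | 2.5% | 5.7% | 6.3% | 7.0% | 7.2% |
| 6 | 54.1 | 32.5 | 6.7% | 10.7% | 25.0% | 28.2% | 28.7% |
| 9 | 80.8 | 56.0 | 11.1% | 15.2% | 39.7% | 44.8% | 45.3% |
| 12 | 106.5 | 79.9 | 15.1% | 19.1% | 50.0% | 56.2% | 56.6% |

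With 375 new cases as the base, the 6-month share is 32.5/407.5 = 8.0%, which is little different.

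**Other time origin.** If survival runs from the first in-window ERCP, the exponential model has no memory. Carried-over patients then have the same one-year survival as new ones (25.0% at m = 6), so there is no inflation.

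**Restenting.** If every entrant's repeat procedure counts as restenting, the proportion ever restented moves from p to (450p + Np)/(450 + Np). That is 42.9% to 44.3%, 60.0% to 62.7%, 69.2% to 72.6%, and 75.0% to 78.8%, or 1.4 to 3.8 points. Restenting within three months of the first ERCP, the longest interval item 19 offers, moves only from 34.8% to 35.4% at m = 6.

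**The case against.** Several points on the other side have force.

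- **Entry only through a repeat ERCP.** A reader might infer that earlier patients must have survived to a second procedure. The text does not say so. Listing is through outpatient and inpatient records, so a clinic visit may suffice. What the text supports is survival into the window. The wider route admits more patients (about 6% to 19%) and weakens the restenting argument.
- **A known direction of bias.** A reader might infer that survival is certainly inflated. That holds only if time runs from the first ERCP. From the in-window ERCP the inflation is nil under the exponential model, and if the hazard rises with time since first stent the bias could be downward. What remains is that the plan does not fix the origin.
- **Restented by definition.** This requires the repeat procedure to be scored under item 19. A return eight months after the first stent fits none of its timing options. If the in-window ERCP is the index, the repeat is not a restenting event at all.
- **Main outcomes.** The protocol does not call survival and restenting its main outcomes. Its general aim is the clinico-demographic profile, and these are two proforma items under one specific objective.
- **The investigators may mean new patients.** Multiplying an annual case count up to a total can be read that way, and nowhere does the plan say that pre-2017 patients will be included. But B.7.2 and B.7.5, followed as written, admit them.
- **Size against sampling error.** At n = 375 the 95% half-width around 25% is 1.96 × √(0.25 × 0.75/375) = 4.4 points, more than the 3.2-point shift at 6-month median survival. This is fair on urgency, but an interval around a biased estimate does not show the bias.

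**Conclusion.** The concern holds in a conditional form. The entry rule admits patients first treated at this hospital before 2017 only if they lived to be listed in the window. Nothing in the plan defines an index ERCP, sets a time origin or allows for late entry.

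If survival is counted from the first ERCP, one-year survival is overstated by about 1, 3, 5 or 6 points for assumed median survival of 3, 6, 9 or 12 months, with carried-over patients making up about 2.5% to 15% of the sample by repeat ERCP. These sizes rest on assumed survival and restenting times, and on reading the 75 a year as new patients. If survival is counted from the first in-window ERCP, the exponential model gives no inflation, but outcomes of first and repeat procedures are pooled as if alike. The restenting effect is smaller and depends on how the repeat procedure is scored.

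This is a modest, avoidable bias in two planned outcome items. It does not undermine the descriptive profile, and the documents do not establish that it will occur or how many patients are involved.

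**What to change.** 1. In B.7.2 and B.7.4, define the index ERCP as the patient's first ERCP for cholangiocarcinoma, checked against the hospital's ERCP register and any record of an earlier stent placed elsewhere.
2. Add the index ERCP date and a prior ERCP or stent field to the proforma, and state that items 19 and 21 are counted from the index date.
3. Restrict the survival and restenting analyses to patients whose index ERCP falls between January 2017 and January 2023.
4. Keep earlier-treated patients in the clinico-demographic description, but tabulate their outcomes separately.

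The cost is one look-back per patient and two extra fields. The two outcome analyses lose about 3% to 15% of patients under the assumed range, or up to about 19% if any visit counts as listing. Stents placed elsewhere will be found only where the records mention them, so some late entry may remain and should be noted in B.12.

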B15.1 Management of specimen/data archiving or left-over

NA

B15.2 Specimen/data sharing plan

NA

C. ETHICAL CONSIDERATION

10.1. Ethical issues	Yes/ No	Justification if yes
a. Are human participants included in the study?	Yes	The study aims to determine the clinico-demographic profile of the patients with cholangiocarcinoma undergoing ERCP in Dhulikhel Hospital. But we will not have face to face interaction, as all the information will be obtained from the medical records.
b. Are vulnerable members of the population required for this research? (includes age under 18, pregnant women etc)	No	
c. Are there any risks involved for the participants? If yes, identify clearly what are the expected risks for the human participants in the research and provide a justification for these risks.	No	
d. Are there any benefits involved for the participants? If yes, identify clearly what are the expected benefits for the participants.	No	

C1. SIGNIFICANCE OF THE STUDY

- The study can reveal some risk factors associated with the particular disease i.e Cholangiocarcinoma. Thus, it can be regarded as a baseline study for conducting any intervention.
- It can also be used as a reference for future study purposes in similar types of study.

C2. BALANCE OF RISK AND BENEFIT

C2.1 Risk of the study and Preventive and alleviative measures for risk

C2.1. Risk management:	
Potential risks identified	Proposed measures to mitigate risks
1. No direct risk/harm to the study participants as medical records will be reviewed primarily for patient data collection.	NA
2. Information on the patient's current status will be gathered via telephone interview (only for the feasible cases) where they may have to spare a few minutes for the data, however, this will take only a few minutes.	Verbal consent will be taken and all the information will be provided to the participants if the interaction is required.

C2.3 Benefits of the study

The study will be helpful to the future researcher to base on this and plan further studies so that we can enhance the prevention and treatment processes.

C3. CONSIDERATION FOR VULNERABLE RESEARCH PARTICIPANTS

Check whether your study involves any of the following vulnerable research participants.

- Prisoners
- Pregnant women
- Mentally ill persons
- Cancer or terminally ill patients
- Neonates/infants/children (aged <18)
- HIV/AIDS patients
- Institutionalized persons e.g. military, students, etc.
- Others (please specify).....

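### The survival item (proforma item 21) cannot code survival of 1–3 months or separate dead, alive and unknown; no source is named for deaths after discharge, and the sections on patient contact contradict each other

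*Combined protocol and SAP*

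**What the plan says.** **Sources of data.** B.8 first states that "data will be collected through a case sheet of the patient and record of ERCP procedure at the department using prepared Per forma". Its second bullet adds: "Data of procedure outcome will be collected via call to the patient". C2.1 row 1 says that "records will be reviewed primarily for patient data collection", and row 2 says that information on the patient's "current status will be gathered via telephone interview (only for the feasible cases"). C4.a describes the call as a short follow-up of patient status with verbal consent. No relative, death record or registry is named.

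**Contact with patients.** B.7.1 says: "Thus, the person will not be contacted directly for the data collection". Row a of the ethics table rules out face-to-face interaction, "as all the information will be obtained from the medical records". C3 says that the study only reviews past records and does not interact directly with patients.

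**Survival item.** Part 3 of the proforma ends with item 21, headed as a survival rate. Its four bands are under 1 month, 3–6 months, 6 months to 1 year, and over 1 year.

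**Population and analysis.** B.7.5 covers January 2017 to January 2023 and plans "total population sampling with an estimated sample size of 375". B.10 lists descriptive statistics, chi-square tests, t-tests and correlation, with no rule for missing status. B.8.2 says: "The proforma will be pretested entering about 10 cases so that we can further modify the proforma".

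**The concern.** Item 21 fails as written for two reasons. A patient who survived 1–3 months has no box to tick. A patient who died at 4 months and a patient last known alive at 4 months get the same tick. Item 11 on the same form offers an unknown option; item 21 does not.

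The source of status is a separate weakness. B.1 describes the disease as fatal and the cases go back to January 2017, so many patients may have died before any call. Records may show deaths in hospital and later visits. For a patient who died after discharge, or who cannot be reached, the plan names no source and no place in the denominator. If deaths are learned of much less often than living patients are reached, and unreached patients are left out, the distribution shifts towards longer survival.

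Finally, an ethics committee that relied on B.7.1 or C3 would understand a records-only study, while one that relied on B.8 or C4 would understand a study with telephone calls.

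**Working it through.** **Inputs.** From the documents: the item 21 bands, the window January 2017 to January 2023 (73 months counted to the end of January 2023), and N = 375. Not in the documents, hence assumed: exponential survival S(t) = 2^(−t/m) with median m of 3, 6 or 12 months, uniform accrual, the date of the calls, and the contact rates. The percentages do not depend on N. (375 equals 75 × 5, while the stated window of six years gives 75 × 6 = 450; that is a separate matter.)

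**1. The uncoded band.** Share of patients = S(1) − S(3). If they are left blank and out of the denominator, the over-1-year share is S(12) / (1 − [S(1) − S(3)]).

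| Median | S(1) − S(3) | Of 375 | True over-1-year share | Share as read |
|---|---|---|---|---|
| 3 months | 0.794 − 0.500 = 0.294 | 110 | 6% | 0.0625/0.706 = 9% |
| 6 months | 0.891 − 0.707 = 0.184 | 69 | 25% | 0.250/0.816 = 31% |
| 12 months | 0.944 − 0.841 = 0.103 | 39 | 50% | 0.500/0.897 = 56% |

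If data collectors instead put these patients in the lowest band, that band reads 1 − S(3) = 29% instead of 1 − S(1) = 11% at a 6-month median. Both effects arise even when every death is known.

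**2. Would the pretest catch it?** The chance that at least one of 10 cases falls in the gap, if survival is known for all ten, is 1 − (1 − share)^10 = 97%, 87% or 66% for medians of 3, 6 or 12 months. So it probably would. It would not supply a status field or a source of deaths.

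**3. Selective ascertainment.** Let r = (share of deaths learned of) / (share of living patients reached). Let the calls fall L months after the window closes, so that time from ERCP to call, u, is uniform on [L, L + 73]. With unreached patients left out,

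over-1-year share = [P(alive, u > 12) + r·P(dead, survived > 12)] / [P(alive) + r·P(dead)].

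For m = 6, L = 12: P(alive) = (6/ln 2)/73 × [S(12) − S(85)] = 0.0296, and P(dead, survived > 12) = 0.25 − 0.0296 = 0.2204. At r = 0.1 the share is (0.0296 + 0.0220)/(0.0296 + 0.0970) = 0.41.

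For m = 6, L = 0: P(alive) = 0.1186 and P(u > 12) = 61/73 = 0.836, so P(dead, survived > 12) = 0.836 × 0.25 − 0.0296 = 0.1793. At r = 0.1 the share is (0.0296 + 0.0179)/(0.1186 + 0.0881) = 0.23.

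Across call dates, m = 6, r = 0.1, true value 25%:

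| L (months) | 0 | 3 | 6 | 12 | 18 | 24 |
|---|---|---|---|---|---|---|
| Over-1-year share | 23% | 28% | 32% | 41% | 34% | 30% |

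Across r, m = 6:

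| r | 0.1 | 0.2 | 0.4 | 0.5 | 0.8 | 1 |
|---|---|---|---|---|---|---|
| L = 6 | 32% | 28% | 25% | 24% | 23% | 23% |
| L = 12 | 41% | 33% | 28% | 27% | 26% | 25% |

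At r = 0.1 and L = 6 or 12, a 3-month median (true 6%) gives 8% or 9%, and a 12-month median (true 50%) gives 60% or 76%. The values below the truth for early calls arise because patients with ERCP less than a year before the call cannot yet be recorded as over 1 year.

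**4. Contact.** B.7.1 and C3 exclude direct contact, and the ethics table says that all information comes from records. B.8, C2.1 and C4 provide for calls with verbal consent. Ruling out face-to-face interaction does not by itself exclude a call, but the other statements do.

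**The case against.** The strongest reply is that the plan has mitigating text and that the bias figures rest on assumptions. Records may well show some deaths. B.8 speaks of a respondent, which could be stretched to include a relative, although the stated call is to the patient. B.12 concedes that a retrospective study may lack wanted information, though it is general and supplies no source of vital status. The place of item 21 under the outcome of ERCP implies ERCP as the time origin, though this is not stated. The pretest would probably expose the missing band. C2.1 says that records are used primarily, so a mix of records and calls seems intended. Text was removed from the documents, so the absence of dates is certain only for the proforma as shown. All of this stands, and it limits the point without removing it.

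Two stronger readings are tempting, and the documents do not support either. A reader might infer that survival will be grossly overstated, because someone who has died cannot answer a call. The model gives 100% over 1 year at r = 0 and L = 12, but that requires that no death is ever learned of, even from records, and it would rest on the 3% of patients still alive (about 11 of 375). The documents give neither r nor a call date, and 12 months is the highest of the call dates tabulated. A reader might also infer that the data would hide the problem. Blank entries in item 21 would show how much is missing. What they would not show is whether a blank means 1–3 months or not reached, or whether a ticked band means death or last contact.

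**Conclusion.** The point holds and should be fixed before data collection. Three parts are certain from the text: survival of 1–3 months has no code, item 21 does not separate dead, alive and unknown, and the statements on patient contact contradict each other. The effect of the missing band depends on the assumed median: 10% to 29% of patients uncoded for medians of 12 to 3 months, with the over-1-year share raised by about 3 to 6 percentage points if they are left out.

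The lack of a source for deaths after discharge is a real gap, but its effect cannot be sized from the documents. With a 6-month median and deaths ascertained at one tenth the rate of the living, the over-1-year share is 23% to 41% against a true 25%, depending on the call date. With near-equal ascertainment there is no material upward bias. These are illustrations under exponential survival and uniform accrual, not estimates.

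Survival is one item under the third of four specific objectives. The clinico-demographic profile is not affected.

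**What to change.** 1. Add a 1–3 month band to item 21.
2. Record date of ERCP, date of death or last contact, and status as alive, dead or unknown. State that survival is counted from ERCP.
3. Define which cases are feasible to call. Allow a consenting next of kin to report a death and its date, with notification to the ethics committee.
4. Keep all eligible patients in the denominator and show the number with unknown status.
5. Report 1-year survival among patients with ERCP at least 1 year before the status date, counting unknowns first as all dead and then as all alive. A documented contact more than 1 year after ERCP counts as known survival.
6. Reconcile B.7.1, the ethics table and C3 with B.8, C2.1 and C4.

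The cost is some protocol and call-script wording, a few proforma fields and one ethics notification; the calls are already planned. There are two downsides. Relatives' dates carry recall error. The bounds may be wide: with a 6-month median, calls at 12 months and 70% of both living and dead ascertained, they run from 0.7 × 25% = 18% to 18% + 30% = 48% (17.5% to 47.5% before rounding). At 90% they run from 23% to 33%. At 70% of the living and r = 0.1 they run from 4% to 95%, which would show plainly that the data cannot support a survival figure.
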